3.3.2 Evaluation Study Design

The evaluation will consist of one baseline assessment and two follow-up assessments. The baseline assessment (**O₀**) of Patient-Physician Relationship percent score of the family physicians' patients of Heratsi and Muratsan Polyclinics will be gathered in August 2015. The follow-up assessment will be done one-month after the training in December 2015 (**O₁**) and seven months after the completion the program (six month after the first follow-up) in June 2016 (**O₂**). A Quasi-experimental, non-equivalent Control Group Design with independent groups will be applied for the proposed evaluation. The chosen design allows us to have a comparison group.

Intervention Group	O₀	X	O₁	O₂
Comparison Group	O₀		O₁	O₂

O₀ - Baseline Data Collection

X – Intervention

O₁ – Follow-up assessment one month after the end of the intervention

O₂ – Follow-up assessment six months after the first follow-up assessment

Threats to Internal Validity: History threat to internal validity will not be a significant issue since programs on leadership for family physicians Armenia are rare; moreover, having a comparison group will address the issue. Maturation can be a threat because the leadership development might not be only due to the intervention (Physician Leadership Development Program) but it might be due to the natural process of the physician acquired some skills during their practice; however, having a comparison group helps to address the issue. Testing cannot be a threat because the survey participants are independent. Instrumentation cannot be a threat, as the questionnaire used for the baseline and two follow-up assessments will be the same. Regression to the mean cannot be a threat because the survey participants are not people with only outlying characteristics related to the outcome variable of interest.

Selection bias can be a threat because there is no randomization of the survey participants into intervention and comparison groups. Moreover, the survey participants in both groups might differ from each other in terms of demographic and severity of disease. Compensatory rivalry can be a threat because the program participants will be aware of the evaluation study. Therefore, the family physicians might change their behavior and be friendlier with their patients. Attrition cannot be a threat because of survey participants are independent groups.

Threats to External Validity: Testing/Intervention interaction cannot be a threat because the assessment will be done on the independent groups. Therefore, the generalizability of evaluation results will not be jeopardized because of baseline measurements. Selection/Intervention interaction is a threat since the selected two primary healthcare centers (Heratsi and Muratsan Polyclinics) cannot represent all the primary healthcare centers in Armenia. The Reactive Situational effect can be a threat because the program participants might outperform due to the fact that they will know about the evaluation. Therefore, the results might not be generalized. Multiple treatments (leadership development programs) interference can be a threat because exposures to this kind of programs might be quite common in other countries. Therefore, the results from Armenia might have limited generalizability.

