3.2 Implementation Plan Synopsis

3.2.1 Program

We proposed to implement the Physician Leadership Development Program to the family physicians of Heratsi polyclinic, which is under the administration of Yerevan State Medical University. During the program, the core training personnel will consist of two physicians who have taken “training of trainers” course. These physician trainers should have a Master of Public Health (MPH) degree from the American University of Armenia. The trainers will take the free online course “Edward Jenner Program” provided by Leadership Academy in National Health Services, United Kingdom.³⁴ The trainers will complete the course and obtain a certificate. On completion of the online program, the trainers will use these materials to teach the family physicians. The trainers will also translate the online program materials into Armenian. The training course includes topics not only about the leadership (as a core component), but also about cooperation, planning, resource management, innovation in patient care, assessment of outcomes of patient care and decision-making.

The program consists of 21 sessions (each 40 minutes), three sessions a week in a seven-week period. The physicians in the primary health centers work on two shifts; Morning shift: (9:00 AM -1:00 PM) and afternoon shift (1:00 PM - 5:00 PM) for six days a week. Each physician has his/her schedule on even and odd days of the week. Separate sessions will be offered to two cohorts on even and odd days of the week. The session will conduct on each day of the week from 2:00 PM until 3:30 PM with a break of fifteen minutes. No session will schedule for Sundays. The sessions will be conducted at the American University of Armenia.

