3.3.2 Study Settings and Target Population

In the intervention group, the target population is the family physicians' patients who have registered in the Heratsi polyclinic and attained treatment. In the comparison group, the target population is the family physicians' patients who have registered in the Muratsan Polyclinic and attained treatment. Heratsi and Muratsan polyclinics are selected for convenience; they both are under the administration of Yerevan State Medical University. Moreover, the organizational culture, administrative proceedings, pay scale, budgeting, and management are similar to each other. The inclusion and exclusion criteria of the survey participants are (Table 1):

Inclusion Criteria:

- a) Being registered with Heratsi or Muratsan polyclinics
- b) Being eighteen year old to sixty-five years old
- c) Visiting family physicians

Exclusion Criteria:

- a) Being registered with these polyclinics after the baseline assessment (exclusively for follow-up assessments)
- b) Patients who participated in the previous assessments in this survey (exclusively for follow-up assessments)

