3.3.3.2 Sampling Scheme

For the selection of survey participants, the project team will use probability systematic random sampling. The survey will be conducted at the polyclinic as an exist survey, just after the patients' visit their family physicians. The survey will be conducted from Monday through Friday for 20 days. The survey hours will be from 09:00 to 13:00 in the respective months of the assessments in both polyclinics. The sample size for baseline and follow-up assessments each group in intervention and comparison is 1,262. To conduct the survey for 1,262 patients in twenty days, approximately sixty-four (64) surveys need to be conducted per day. The average numbers of patients visit the family physicians per weekday will be obtained (July 2015) from the administrators of the polyclinics. Then the interval between the survey participants will be calculated by dividing the number of visitors by nine for the baseline and follow-up assessments. After the patients' visit to the polyclinic, the supporting staff will approach to the patients. The patients, who have visited family physicians in the Heratsi and Muratsan polyclinics, will be asked to participate. The data will be collected through a self-administrated survey questionnaire. The supporting staff will collect the data from both polyclinics.

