3.3.4 Variables

The dependent variable of interest is Patient-Physician Relationship percent score, which is a numerical continuous outcome variable (Table 2). It is measured through 25 questions. The response options for each statement consists of nine levels of agreement between “Strongly Disagree” to “Strongly Agree”. The patient-physician relationship score ranging from 25-225 from the questionnaire will be re-calculated to patient-physician relationship percent score ranging from 11% to 100%.

The main independent variable of interest is being from Heratsi (intervention) or Muratsan (comparison) polyclinics. It is a nominal dichotomous type of variable. The special identification number of the questionnaire will identify the information.

The control variables suggested by literature include: participant’s sex, age, socio-economic status, educational status, and marital status.^{31,35,38,39} Literature shows that the above-mentioned control variables can influence the desired outcome of variable.^{31,35,38,39}

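### With one trained and one untrained clinic, the comparison group cannot remove events or drift confined to one clinic, and the stated alpha and power cover patient sampling only

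*Protocol*

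**What the plan says.** The Program section (3.2.1) trains one clinic: "We proposed to implement the Physician Leadership Development Program to the family physicians of Heratsi polyclinic". Study Settings and Target Population takes the comparison group from one other clinic, and explains the choice: "Heratsi and Muratsan polyclinics are selected for convenience; they both are under the administration of Yerevan State Medical University". It also describes the two clinics as alike in culture, pay, budgeting and management. The Variables section (3.3.4) defines exposure by clinic: "The main independent variable of interest is being from Heratsi (intervention) or Muratsan (comparison) polyclinics".

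Evaluation Study Design names the design openly: "A Quasi-experimental, non-equivalent Control Group Design with independent groups will be applied for the proposed evaluation". Under threats to internal validity it expects no significant problem from history. It gives two reasons: programmes on "leadership for family physicians Armenia are rare; moreover, having a comparison group will address the issue". On maturation it is more careful, and says only that the comparison group is of help. It concedes selection bias between survey participants and compensatory rivalry. Under external validity it concedes that two centres cannot stand for all of Armenia.

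The Sample Size section (3.3.3.1) uses 1.96 and 1.28, that is, two-sided 5% and 90% power, with patient variance only. On fieldwork, the Sampling Scheme section (3.3.3.2) says: "The survey hours will be from 09:00 to 13:00 in the respective months of the assessments in both polyclinics". The supporting staff are to collect the data at both sites.

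**The concern.** Neither reason given for dismissing history is sufficient. The rarity of other leadership training excludes one kind of event. History also includes a new manager, a changed appointment system, physicians leaving, or a change in who hands out the questionnaire. A comparison group cancels such an event only if it reaches both clinics in the same way.

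An event or drift at one clinic alone changes the Heratsi-Muratsan contrast exactly as a programme effect would. The baseline survey removes stable differences between the clinics but not changes that arise after it. The five control variables describe patients, so they cannot absorb a clinic-level event.

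What is at stake is the conclusion. A significant difference could be read as a tested effect of the training, when the test can support only a difference between two named clinics.

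**Working it through.** **1. The plan's own figure.** The inputs are those printed in the Sample Size section: z-values 1.96 and 1.28, SD 2.5 in both groups, difference 0.585.

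(1.96 + 1.28)² × (2.5² + 2.5²) / 0.585² = 10.4976 × 12.5 / 0.342225 = 383.4, or 384 per group.

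The printed 1198 does not follow. It appears if the two variances are multiplied instead of added: 10.4976 × 39.0625 / 0.342225 = 1198.2. The step to 1262 does follow (1198 / 0.95 = 1261.1, rounded up). The slip is a separate matter and does not affect this point. What matters here is that the formula has no term for clinic.

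**2. Degrees of freedom.** There are two clinics and two group means to estimate, so 2 − 2 = 0 degrees of freedom remain for variation between clinics. This needs no assumption, and more patients do not change it.

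**3. Illustration of size.** The notation is:

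- n = 1198 per clinic per wave (Sample Size section).
- s = patient SD on the percent score. **Assumed** 15; the protocol states 2.5.
- τ = SD of clinic-specific movement from wave to wave. **Assumed**; the protocol gives none.

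The contrast is the difference in changes between clinics, which is the most favourable one because stable clinic differences cancel. It uses four clinic-by-wave means, so:

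- Patient-only SE = s × √(4/n) = 15 × √(4/1198) = 0.867
- SE with clinic movement = √(0.867² + 4τ²)
- Rejection rate with no programme effect = 2 × [1 − Φ(1.96 × patient-only SE / SE with clinic movement)]

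| τ (points) | SE with clinic movement | Rejection rate at nominal 5% |
|---|---|---|
| 0.1 | 0.890 | 6% |
| 0.2 | 0.955 | 8% |
| 0.5 | 1.323 | 20% |
| 1 | 2.180 | 44% |
| 2 | 4.093 | 68% |

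For τ of 0.5, 1 and 2, s = 10 gives 33%, 59% and 78%, and s = 25 gives 11%, 25% and 51%. With the protocol's s = 2.5 the patient-only SE is 0.144, and τ of 0.1, 0.25 or 0.5 gives 25%, 59% or 78%.

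**4. Limit with unlimited patients.** The SE cannot fall below 2τ. At τ = 1 the 95% half-width is at least 1.96 × 2 = 3.9 points, against a planned gain of 64.07 − 55.71 = 8.36.

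**5. The first follow-up alone.** This is the contrast by which the Sample Size section defines success. Its patient variance is 2s²/n and its clinic-by-wave variance 2τ², so the rates equal those above only if the clinics never differed. Any stable difference adds to them. With s = 15, τ = 0.5 and an assumed stable between-clinic SD of 1 point, the SE with both clinic components is √(0.613² + 0.5 + 2) = 1.696 against a patient-only 0.613, and the rate rises from 20% to 48%.

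**The case against.** The strongest reply is that the protocol hides little. It presents a quasi-experimental pilot with non-equivalent groups, admits convenience selection, and concedes selection bias, rivalry and limited generalisability. The shared administration may well keep local drift small. This stands as mitigation. It does not close the gap: selection bias is conceded only as a difference between survey participants, generalisability is a different question, and similarity of drift cannot be tested with one clinic per group.

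A second reply is that for two fixed clinics a local event is bias, not random variation, and the patient-level error rate is then valid for the difference between those clinics. That is right, and it is the scope that the plan should state. It also means that the percentages above are illustrations. A reader might infer that this trial has a 44% false-positive rate; the documents do not support that, because τ is unknown and s = 15 is not the protocol's value. At τ = 0.1 the rate is close to nominal.

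Two further readings go too far. A reader might infer that the plan claims the comparison group disposes of all drift; on maturation it claims only help. A reader might also infer that a result of the planned size would mean nothing. At 8.36 points the illustrative SEs for τ = 0.5, 1 and 2 give ratios of 6.3, 3.8 and 2.0, so the threat is mainly to smaller differences.

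On staffing, the protocol assigns nobody to a clinic and the questionnaire is self-administered. Fixed staff at each site is therefore a risk inferred from simultaneous fieldwork, not something the protocol states.

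**Conclusion.** The point holds. The statement that a comparison group will address history is wrong for anything confined to one clinic, because clinic and programme are the same variable in this design. The alpha and power in the Sample Size section describe patient sampling error for the difference between Heratsi and Muratsan and nothing wider. Both conclusions rest only on the stated design and the 0 degrees of freedom.

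The size is not determined by the documents. Under the assumptions shown (s = 15, difference in changes), the rate runs from about 6% at τ = 0.1 to 68% at τ = 2, and the first follow-up contrast alone is at least as bad. The pilot can proceed, but its text should not claim a protection that the design lacks.

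**What to change.** 1. In Evaluation Study Design, state that the comparison group removes only events and trends common to both clinics, and that clinic-specific history and maturation remain as threats.
2. In Sample Size, state that alpha and power refer to patient sampling error for the difference between these two named clinics.
3. Word the objectives and the conclusion as change at Heratsi relative to Muratsan, not as a tested programme effect. The third measurable objective is already a between-clinic comparison, so this is a short edit.
4. In Sampling Scheme, rotate the same supporting staff between the two clinics by day, so that staff do not coincide with group.
5. If false-positive rates are quoted anywhere, label them as illustrations and state the assumed SDs.

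It may be tempting to use questionnaire items 3 and 4 (the patient's own health and lifestyle) as a negative control that decides attribution. This is not advised. They are two of the 25 scored items, and local events that change views of the doctor could leave them flat, which would reassure falsely.

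The cost is protocol wording and a staff rota, with no extra data. The downside is a more modest claim. These changes do not remove the confounding; only several clinics per group, analysed at clinic level, would provide the missing replication.

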3.3.3 Questionnaire

In order to measure the variables of interest for the evaluation, the study team proposes to use a self-administrated questionnaire (Appendixes 3 and 4). The questionnaire consists of validated questions to measure patient-physician relationship score from patients' perspective³³ and questions to measure socio-demographic characteristics of the survey participants.³⁷ The validated questionnaire to measure patient-physician relationship from patients' perspective is adopted from "patient measure of the doctor-patient caring" questionnaire by Buetow et al. (2011).³³ The self-administrated questionnaire for the

proposed project's evaluation consists of thirty questions. Among these thirty questions, twenty-five questions measure the patient-physician relationship score and five questions measure socio-demographic characteristics of the survey participants. In the questionnaire, the twenty-five questions measuring patient-physician relationship are grouped into five domains. Each domain consists of five questions.

The domains are as follows:

- 1) Patient's Self Care
- 2) Doctor's Self-care
- 3) Patient cares about the doctor
- 4) Patient empathy for the doctor
- 5) Doctor cares about the patient.

Response options have nine levels of agreement with each statement from “Strongly Disagree” to “Strongly Agree.” The patient-physician relationship score is the numerical continuous variable, which is a dependent variable. In the self-administered survey questionnaire, the socio-demographic questions refer to sex, age, marital status, socio-economic status, and educational status. The self-administered questionnaire will take about 10 minutes to complete and provides anonymity. To preserve the anonymity, no personal identification information will be collected. Instead, each questionnaire will have a special identification number. The special identification number will consist of six characters. The first character of the identification number will feature one English alphabet, i.e. “H” or “M”. Latter is to represent the polyclinic where the survey participant took the survey. The second character of the identification number will feature one Arabic number, i.e. “0” or “1” or “2”. The numbers “0” represent the baseline assessment and, “1” and “2” represent two follow-up assessments respectively. The other four characters of the identification number will feature Arabic numbers, which will be the numbers of the survey participant. For example, if

“H20604” is the special identification number on the questionnaire, then it implies that the survey participant is from Heratsi polyclinic, who took the survey in second follow-up assessment as 604th participant.

The self-administered survey questionnaire was translated from English into Armenian by two different certified translators and later both copies of the Armenian versions were compared, the most appropriate translated version was considered. The Armenian version of the questionnaire content consistency was reviewed by second year Masters of Public Health program’s students at AUA who are Armenian native speakers. The translated Armenian version of the self-administered survey questionnaire will be pretested among ten participants. The pretest will be conducted among the patients who visited family physicians in a selected polyclinic.

3.3.4 Variables

The dependent variable of interest is Patient-Physician Relationship percent score, which is a numerical continuous outcome variable (Table 2). It is measured through 25 questions. The response options for each statement consists of nine levels of agreement between “Strongly Disagree” to “Strongly Agree”. The patient-physician relationship score ranging from 25-225 from the questionnaire will be re-calculated to patient-physician relationship percent score ranging from 11% to 100%.

The main independent variable of interest is being from Heratsi (intervention) or Muratsan (comparison) polyclinics. It is a nominal dichotomous type of variable. The special identification number of the questionnaire will identify the information.

The control variables suggested by literature include: participant’s sex, age, socio-economic status, educational status, and marital status.^{31,35,38,39} Literature shows that the above-mentioned control variables can influence the desired outcome of variable.^{31,35,38,39}

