3.3 Evaluation Plan Synopsis

Evaluation of the Physician Leadership Development Program is an important component of this grant proposal. The evaluation plan consists of one baseline and two follow-up assessments of the both intervention and comparison groups. These assessments are to assess the outcomes of the Physician Leadership Development Program of the proposed project. The evaluation is to quantify patients’ perspective of Patient-Physician Relationship through a quantitative method by the survey questionnaire.

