3.3.1 Measurable Objectives

- A month after the end of the program (December, 2015), the Patient-Physician Relationship percent score of the physicians' patients will increase by 15% compared to the baseline percent score of the intervention group (August 2015).³⁵
- Six months after the first follow-up assessment (June 2016), the Patient-Physician Relationship percent score of the physicians' patients will increase by 17% compared to the baseline percent score of the intervention group (August 2015).³⁵
- Six months after the first follow-up assessment (June 2016), the Patient-Physician Relationship percent score of the physicians' patients of the intervention group will be higher by 10% compared to the comparison group.³⁵

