3.3.3 Sampling Scheme

3.3.3.1 Sample Size

The student investigator calculated the sample size with the formula for two group comparison of means, exposed and unexposed groups for Cohort studies³⁶ by Epi-Info® -7 software. The outcome of the project is considered as a success if the difference between the intervening and comparison group in the first follow-up (O_1) assessment is 15% improvement in the patient-physician relationship percent score. From the existing literature of the other studies,³⁵ we assumed the baseline percent score of the patient-physician relationship to be 55.71% for both groups. After the intervention, the patient-physician relationship percent score is expected to increase to 64.07% in the intervention group in the first follow-up assessment (O_1).

The sample size is calculated based on the expected changes in the mean patient-physician relationship percent score in the intervention group of 15%. For variance, student investigator assumed that in both groups it will be equal. From a similar type of study,³⁵ the standard deviation of 2.5 was taken for calculation. Hence, the sample size was calculated to be one thousand one hundred and ninety eight (1198) in the intervention group and one thousand one hundred and ninety eight (1198) in the control group.

$$n_1 = n_2 = \frac{(Z\alpha/2 + Z\beta)^2 (\sigma_1^2 + \sigma_2^2)}{\Delta^2}$$

$$1198 = \frac{(1.96 + 1.28)^2 (2.5^2 + 2.5^2)}{(0.585)^2}$$

The literature shows that the response rate for similar types of evaluation studies have a response rate of 95%. Taking into consideration this information the estimated the sample size should be one thousand two hundred and sixty-two (1262) in each group.

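### No stated objective or success rule compares change in Heratsi with change in Muratsan, although both polyclinics are surveyed at baseline and at both follow-ups

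*Protocol*

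**What the plan says.** **Data.** Section 3.3 (Evaluation Plan Synopsis): "The evaluation plan consists of one baseline and two follow-up assessments of the both intervention and comparison groups". The Evaluation Study Design section adds: "A Quasi-experimental, non-equivalent Control Group Design with independent groups will be applied for the proposed evaluation". It dates the assessments to August 2015, December 2015 and June 2016. It relies on the comparison group against history and maturation, and it concedes that selection bias is possible because the groups are not randomised and may differ in demographics and disease severity.

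**Objectives (3.3.1).**
- Objective 1, at O1: the score "will increase by 15% compared to the baseline percent score of the intervention group".
- Objective 2, at O2: the score "will increase by 17% compared to the baseline percent score of the intervention group".
- Objective 3, at O2: the score of the "patients of the intervention group will be higher by 10% compared to the comparison group".

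**Success rule (3.3.3.1).** The project succeeds if the two groups differ at O1 by a 15% improvement. On the starting point: "we assumed the baseline percent score of the patient-physician relationship to be 55.71% for both groups". Heratsi is expected to reach 64.07% at O1, and the SD is taken as 2.5.

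**Analysis (3.3.4, 3.3.5, Table 2).** "The main independent variable of interest is being from Heratsi (intervention) or Muratsan (comparison) polyclinics". The control variables are sex, age, socio-economic status, education and marital status. The methods are the t-test, chi-square test and linear regression. Assessment wave is not listed as a variable.

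**The concern.** A comparison group measured before and after training lets the evaluation subtract two things at once: the standing difference between the clinics and the change over time that both share. Each stated contrast subtracts only one of them.

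Objectives 1 and 2 leave out Muratsan. A rise in Heratsi from any cause between August and December, or between August and June, would meet them. The eligible population also shifts between waves, because the follow-ups exclude earlier participants and patients registered after August 2015. That happens in both polyclinics, but these two objectives do not use Muratsan to allow for it.

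Objective 3 and the O1 success rule leave out the baseline. The polyclinics were chosen for convenience, one per arm, so a clinic whose patients already score higher would appear as a successful programme. The protocol could then declare success on a trend or on a pre-existing gap, although the data needed to correct for both, given parallel trends, are planned.

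**Working it through.** **1. The plan's own figures.**
- Expected O1 score: 55.71 × 1.15 = 64.07, so the planned effect is 64.07 − 55.71 = 8.36 points.
- Sample size: the printed formula gives (1.96 + 1.28)² × (2.5² + 2.5²) / 0.585² = 383.4, so 384 per group, not 1,198. The figure 1,198.2 appears if the two variances are multiplied instead of added. That is a separate point; 1,198 is used below only as the planned number.
- Inflation: 1,198 / 0.95 = 1,261.05, so 1,262, as stated.

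**2. What each contrast estimates.** Let τ be the programme effect, g the change over time common to both clinics, b the standing Heratsi-minus-Muratsan gap not explained by the covariates, and s any shock specific to one clinic.

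| Contrast | Where | Estimates |
|---|---|---|
| Heratsi follow-up − Heratsi O0 | Objectives 1, 2 | τ + g + s |
| Heratsi − Muratsan at follow-up | Objective 3, O1 success rule | τ + b + s |
| Change in Heratsi − change in Muratsan | Not stated | τ + s |

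The first is clean only if g = 0, the second only if b = 0. The sample-size section sets the baseline gap to zero by assumption. The third needs neither condition, but requires that the clinics would otherwise have moved in parallel.

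**3. Size of the bias (assumed gaps).** The documents give no baseline gap, so a range is shown against 8.36 points: 1/8.36 = 12%, 3/8.36 = 36%, 5/8.36 = 60%.

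**4. Chance of a significant result with τ = 0**, at 1,198 per group. SE = SD × √(2/1,198). The shift is b for the contrast after training, or g for the before-after change.
- SD 2.5 (the plan's): SE = 0.102. A 0.5-point shift gives 0.5/0.102 = 4.9 SEs, so probability 0.998.
- SD 10 (assumed): a 1-point shift gives 0.69 and a 2-point shift 0.998.
- SD 20 (assumed): a 2-point shift gives 0.69.
- Difference in changes: 0.05, if trends are parallel.

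**5. Precision of the difference in changes.** Four independent samples give SE = SD × √(4/n), which is √2 = 1.41 times that of the two-sample contrast.
- n = 1,198 per cell, SD 2.5: SE = 0.1445; 0.585/0.1445 = 4.05; power 98%.
- 90% power for 0.585 needs 768 per cell, against 384 for the contrast after training only.
- For 8.36 points at 90% power: 4 per cell at SD 2.5; 61, 136 or 241 at assumed SDs of 10, 15 or 20.

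**6. Budgeted numbers.** Six cells of 1,262 are 7,572 questionnaires. Appendix 6 pays for 1,018 and bases data entry on 1,080, which is about 170 to 180 per cell. Power for 0.585 at SD 2.5 is then about 33% to 35%. For 8.36 points at 180 per cell it is 96% at an assumed SD of 15 and 80% at 20.

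All these power figures ignore clustering by physician.

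**The case against.** **Concurrent comparison.** A reader might infer that no stated contrast handles history or maturation. The documents do not support that. Objective 3 and the O1 rule compare the polyclinics at the same time, which cancels trends common to both. What remains is selection, which the protocol names as a threat and partly addresses through five covariates. Disease severity, which it also names, is not among them.

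**Use of the baseline.** It would also be too strong to say that the baseline is unused. Objectives 1 and 2 use Heratsi's, and Appendix 5 schedules data analysis in September 2015, before any follow-up. The accurate statement is that Muratsan's baseline enters no stated contrast.

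**Model detail.** Section 3.3.5 lists families of methods and does not exclude a wave term; an analysis plan could supply one. This stands, so the missing term is not in itself the error. The objectives and success rule, however, are fixed in the protocol, and a later model would not change what they count as success.

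**An implied trend.** One could read the targets as predicting a rise in Muratsan: 55.71 × 1.17 = 65.18, and 65.18/1.10 = 59.26, so 3.55 of the 9.47-point gain in objective 2 (37%) would not be programme effect. This treats two separate targets as a joint prediction and reads 10% as relative. Read as points, Muratsan would be at 65.18 − 10 = 55.18, below its assumed baseline. The O1 planning figures imply no change in Muratsan. The 37% is not relied on here.

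**Conclusion.** The point holds. Every stated objective and the success rule is either an uncontrolled before-after change or a contrast after training only, in a design the protocol itself calls non-equivalent. None compares the two changes from baseline.

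The actual bias cannot be known from the documents: the 12%, 36% and 60% rest on assumed gaps of 1, 3 and 5 points. At the plan's SD of 2.5 and 1,198 per group, even a 0.5-point gap or trend would almost certainly be declared significant with no programme effect.

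A reader might infer that a difference in changes would remove all bias. It would not. It rests on parallel trends, and with one polyclinic per arm an event specific to one site cannot be separated from the programme.

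**What to change.** 1. Restate the three objectives and the O1 success rule as change from baseline in Heratsi minus change from baseline in Muratsan, with each target marked as percentage points or relative per cent.
2. Make the primary analysis one linear model on all three assessments: percent score on polyclinic, wave (O0, O1, O2), polyclinic × wave, and the five listed covariates. Polyclinic × O1 is primary and polyclinic × O2 secondary. Before-after changes within each polyclinic can stay as description.
3. State the parallel-trends assumption, and that site-specific shocks cannot be separated from the programme effect with one polyclinic per arm.

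**Cost.** No new data item is needed: the questionnaire number already codes polyclinic and wave for every planned record. The price is the 1.41-fold standard error, which is affordable at 1,198 per cell. If the budgeted questionnaire count is the real ceiling, power for 0.585 is lost, so the budget and the planned sample must be reconciled before the precision of this contrast is claimed.
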